HIPAA	Health Insurance Portability and Accountability Act of 1996
HUC	Health Pod Coordinator/UCA Monitor
ICF	Informed Consent Form
IEC	Independent Ethics Committee
IRB	Institutional Review Board
IRL	In Room Locator
IRT	In Room Tablet
PI	Principal Investigator
PLS	Palarum Local Server
PUP™	Patient is Up Fall Prevention System
RSSI	Receive Signal Strength Indicator
RTLS	Real Time Location System
PCS	Palarum Cloud Service
SAE	Serious Adverse Experience
WIRB	Western Institutional Review Board

PROTOCOL SYNOPSIS

TITLE	Testing the Effectiveness of a Fall Prevention System
SPONSOR	[name] PhD
FUNDING ORGANIZATION	Palarum, LLC
NUMBER OF SITES	1 Site on 3 floors of the Ohio State University Wexner Center Brain and Spine Hospital; (8 South, 9 South, 10 South, 8 East, 9 East & 10 East)
RATIONALE	
Each year, between 700,000 and 1,000,000 people in the United States fall in a healthcare environment (Agency for Healthcare Research and Quality, 2015). Falls can have a widespread and significant impact on health, can be deadly, and often result in high costs. Falls with serious injury are consistently among the Top 10 sentinel events reported to The Joint Commission's Sentinel Event database (The Joint Commission, 2015). The average 200-bed hospital might log 300 patient falls a year (based on 5 patient falls per 1000 patient days), which results in \$10,200 per fall in medical costs annually – or more than \$3 million. (Agency for Healthcare Research and Quality)
 
The best way to reduce the number of falls is to prevent them. A whole marketplace of bed and chair alerts and other devices has been developed to address the need, yet the numbers increase. On a busy patient floor, nurses lose valuable seconds just figuring out which patient's bed alert is sounding. We expect research to show that the Palarum PUP™ System reduces the incidence of falls.

STUDY DESIGN	Single arm trial
PRIMARY OBJECTIVE	To determine if the fall rate (as measured by falls per 1000 patient days) for patients designated “fall risk” decreases with the use of the intervention (Patient is UP fall prevention technology [PUP™]) when compared to historical NDNQI data for the prior 12 months (“Benchmark Data”) from nursing units where the intervention is being undertaken.

SECONDARY OBJECTIVES	
 1. To reduce the incidence of false alerts, <5%. Our goal is a high reliability notification system. 2. To provide positive alert reliability of 95%. Our goal is to reduce alert fatigue with nurses. To determine number of alerts sent out; what is the frequency of these patient safety events (i.e.), fall risk patient up, out of bed, unassisted 3. To gather compliance data and response times from alert to caregiver response.
NUMBER OF SUBJECTS	2500 patients
SUBJECT SELECTION CRITERIA	
Inclusion Criteria: All risk fall patients, eighteen years of age or older, who are admitted to the OSU Brain and Spine Hospital on Floors 8 South, 9 South, 10 South, 8 East, 9 East or 10 East. Patients will undergo a pre-assessment as per OSUWMC procedure to determine if they are of fall risk.
 
Exclusion Criteria: Patients whose medical condition as assessed by the PI prohibits their participation in the program, which would include among others the following: patients who lack the capacity to consent that do not have an Legally Authorized Representative (LAR), patients with an anatomy or wound issue on their feet or around their calves that would bar them from wearing socks on either foot, and/or patients for whom the sock would impede medical treatment.

TEST PRODUCT, DOSE, AND METHOD OF USE	
Test Product: Palarum LLC's, PUP™ (Patient is Up) System
 
Dose: N/A
 
Method of Use:
 
The Study site, the OSU Wexner Center Brain and Spine Hospital, is located on three contiguous floors with each floor being made up of two units or Pods designated East and South. Following commencement of the study, and throughout its duration, Pods assigned to the Study will only utilize the Palarum Fall Prevention System and a monitored PUP™ sock as the standard of care intervention for fall prevention in accordance with its operating instructions and procedures. The Implementation Team for the Study will consist of the PI, the Nurse Managers and Staff, allied health professionals as may be assigned to the Pods during the course of the Study.
 
The Palarum Fall Prevention System is made up of seven tangible elements connected by Wi-Fi and/or BTLE: an inpatient room

	
Android tablet (IRT), a nurse station Android monitor (HUC), a local server (PLS), a cloud server (PCS), a Bluetooth Low Energy beacon(s), an Android smart notification device, and an e-textile sock connected sensor transmitter (PUP™ sock).
 
The PUP™ sock monitors and transmits pressure, force, acceleration and motion data to IRT and PLS, and HUC and PCS. This data is evaluated and validated by an Android application on the IRT to determine whether or not a fall risk patient is standing unaccompanied by a caregiver. If a monitored patient is standing unattended, the PLS locates and alerts the Smart Notification Devices of the five (5) closest healthcare providers and the HUC using the beacon technology.
 
Alerts are terminated by the Smart Notification Device and PLS based on caregiver proximity to the patient. All data, alerts, suspensions, terminations and notifications are recorded by the PCS. On a daily basis, PCS reports are produced which contain data for each patient enrolled, number of alerts, excessive alerts, and caregiver response time, as well as summaries by Pod and entire facility.
 
All Brain and Spine Hospital patients will be evaluated as to fall risk using the current fall risk assessment procedures employed by OSU Medical Center and administered in the usual and customary fashion upon evaluation on the floor and Pod.
 
Any patient fall is to be reported and evaluated following current processes and procedures developed by the OSU Brain and Spine Institute as maintained with IHIS.
 
If a fall risk patient is admitted to the unit and is not otherwise disqualified by the Study Exclusion Criteria, the patient and/or LAR in form of a Patient Consent document, will be given information about and the opportunity for the patient to participate in the Study. If the patient or legal surrogate declines participation, the patient will receive standard of care provided prior to the Study.
 
Upon receiving a consent to participate, the patient will be fitted with a monitored PUP™ sock sized to the patient's foot from the Study inventory, and thereafter enrolled by a caregiver in the Palarum Fall Prevention System using an Android application on the IRT. The Palarum Fall Prevention System and PUP™ sock thereafter monitor the patient's activity 24x7 throughout the patient's entire length of stay. During the patient's stay, the PUP™ sock will be evaluated daily for proper fit, patient comfort, and patient safety. Upon discharge or transfer, the patient is un-enrolled from the system again

--	---

	
utilizing the IRT. All patient relevant fall data, including system performance, is collected and stored in the PCS for future study and evaluation. Any patient fall is to be reported and evaluated following current OSU Medical Center processes and procedures independent of the Palarum Fall Prevention System.
 
Technical support for the Palarum Fall Prevention system is available by phone at [name] [contact] and email, [contact], 24x7. If there is a Palarum Fall Prevention System outage each Intervention Group Pod should follow policies related to downtime procedures for fall risk patients.

CONTROL PRODUCT, DOSE AND ROUTE OF ADMINISTRATION	N/A
DURATION OF SUBJECT PARTICIPATION AND DURATION OF STUDY	Duration: Once a patient has been placed in the fall risk protocol, the patient will remain in the study until a nurse removes the patient from risk fall status or the participant has been discharged from the hospital.
CONCOMITANT MEDICATIONS	
Allowed: YES
 
Prohibited: NONE

EFFECTIVENESS EVALUATIONS	
Effectiveness evaluation data will be collected by the Palarum Fall Risk System, and incorporated and integrated with patient diagnosis, co-morbidities, and other medical data within REDCap including:
 
 1. Enrollment Data 
 a. Patient Identifier/MRN b. Patient Weight c. Patient Sock Size (S-M-L-XL) d. Sex e. Pod and Room/Bed f. Date g. Time h. Sock Number i. Sensor Number 2. Event Logs 3. Time of stand alert 4. Time to clear 5. Who cleared stand 6. Manual or Automatic termination 7. Accelerator and Gyroscopic Data surrounding each stand event

	8. Pressure on foot 9. Motion of patient
PRIMARY ENDPOINT	Fall rate per patient days within the study sample population
SECONDARY ENDPOINTS	
As collected by the Palarum Fall Prevention System, validated by manual audits of thereof, and integrated with REDCap,
 
 • Rate of false alerts • Rate of fall related patient safety events • Time to respond to alert • Pressure on foot • Motion of patient • Alert fatigue analyzed and measured by alert responded/alerts generated over time. • Notification system alerts only the closest five caregivers when a fall risk patient is up • Time to staff notification (latency) when a fall risk patient is up and unattended • Time to clear data • Identification of caregiver clearing alert • Determination of manual or automatic termination
OTHER EVALUATIONS	N/A
SAFETY EVALUATIONS	Incidence of adverse events arising use of device
PLANNED INTERIM ANALYSES	N/A
STATISTICS Primary Analysis Plan	
The primary endpoint for this study is the number of patient falls. This will be expressed as a falls incidence rate, i.e., number of falls per patient days where patient days are counted from the initiation of the PUPTM System until discharge or removal from the fall risk protocol. Using a one-sided one-sample test for Poisson means, we will test whether the observed fall rate is less than the historical rate of 0.004. This test will be conducted at the alpha=0.1 level. Results will be presented as the fall rate and the corresponding one-sided 90% confidence interval which will provide an upper bound for the fall rate.

Rationale for Number of Subjects	The primary endpoint of the trial is the patient fall rate per patient days. Comparing to a historical rate of 0.004 using a one-sided test of Poisson means, we have at least 70% power to detect a 25% reduction in the fall rate at alpha level 0.1 with 2360. Assuming a dropout rate of 5%, we will enroll 2500 patients into the study.
---	---

1 BACKGROUND

The PUP™ System is designed to monitor patient activity in a hospital, clinic, nursing home, or other facility where a patient may be receiving care.

The System includes pressure sensors incorporated into the toe and heel of a sock using both pressure sensitive fibers and also a Bluetooth transmitter affixed to the exterior of the sock in the ankle region. After the caregiver assists the patient in putting on the PUP™ socks, the caregiver will enter the appropriate patient data into the dedicated in-room PUP™ tablet to associate the patient with the specific sensor. When the patient gets out of bed and steps on the floor, pressure is detected by the sock sensors which trigger an alert signal to the PUP™ tablet. This alert is displayed locally in the patient's room on the PUP™ tablet and can be dismissed by a caregiver present in the room with the patient, as appropriate. The in-room PUP™ tablet also relays the alert signal to a local Palarum server which sends the alert signal to both a monitoring device located at the nursing station as well as to notification devices being worn by select caregivers. The sock also includes a sensor for motion detection for power-saving purposes. If the patient is idle for a specified amount of time, the device enters a power-saving mode. Once motion is detected, the system 'wakes' in order to be able to detect whether pressure is applied to the sock indicating that the patient is standing or attempting to get out of bed.

The system can support monitoring of sensors for multiple patients, allowing display of sensor status for multiple patients on the tablet app.

1.1 Overview of Research

Each year between 700,000 and 1,000,000 people in the United States fall in a healthcare environment (Agency for Healthcare Research and Quality, 2015). Falls can have a widespread and significant impact on health, can be deadly, and often result in high costs. Falls with serious injury are consistently among the Top 10 sentinel events reported to The Joint Commission's Sentinel Event database (The Joint Commission, 2015). The average 200-bed hospital might log 300 patient falls a year (based on 5 patient falls per 1000 patient days), which results in \$10,200 per fall in medical costs annually – or more than \$3 million.

Falls are one metric that Medicare now uses to measure hospitals on patient safety. Not meeting the fall metric will trigger a reduction in the hospital's cost reimbursements.

While one in three hospitalized Americans, aged 65 and over falls every year, elderly patients are not the only ones vulnerable to falling in health care facilities. Any patient of any age or physical ability can be at risk for a fall due to medical condition, medications, surgical procedures or diagnostic testing. Falls increase the length of inpatient stays by 6.3 days and hospital charges by \$14,000. (The Joint Commission, 2015).

Most facilities have tried to address falls with traditional motion detection systems, room sitters, and enhanced training, but falls continue to be a quality of care and cost issue. Traditional motion detectors can result in a false alert, which can lead to nurses or other

hospital workers tuning out alerts or turning them off. One hospital executive said they spent \$4.2 million on patient sitters last year

2 STUDY RATIONALE

Palarum LLC (“Palarum”) has designed and developed a wireless and “smart” fall prevention system and desires to have the effectiveness of the system evaluated by The Ohio State University Wexner Medical Center (“OSU”) through a disciplined and structured product evaluation process.

Each year between 700,000 and 1,000,000 people in the United States fall in a healthcare environment (Agency for Healthcare Research and Quality, 2015). Falls can have a widespread and significant impact on health, can be deadly, and often result in high costs. Falls with serious injury are consistently among the Top 10 sentinel events reported to The Joint Commission’s Sentinel Event database (The Joint Commission, 2015). The average 200-bed hospital might log 300 patient falls a year (based on 5 patient falls per 1000 patient days), which results in \$10,200 per fall in medical costs annually – or more than \$3 million. (Agency for Healthcare Research and Quality).

Falls are one metric that Medicare now uses to measure hospitals on patient safety. Not meeting the fall metric will trigger a reduction in the hospital’s cost reimbursements.

While one in three hospitalized Americans aged 65 and over falls every year, elderly patients are not the only ones vulnerable to falling in health care facilities. Any patient of any age or physical ability can be at risk for a fall due to medical condition, medications, surgical procedures or diagnostic testing. Falls increase the length of inpatient stays by 6.3 days and hospital charges by \$14,000. (The Joint Commission, 2015).

Falls represent both a patient safety priority and an economic priority for healthcare organizations. A fall may result in fractures, lacerations, or internal bleeding, leading to increased health care utilization. As of 2008, the Centers for Medicare & Medicaid Services (CMS) does not reimburse hospitals for the extra care associated with an inpatient fall and the trauma associated with it. (The Joint Commission, 2015).

The best way to reduce the number of falls is to prevent them. A whole marketplace of bed and chair alerts and other devices has been developed to address the need, yet the numbers creep up. On a busy patient floor, nurses lose valuable seconds just figuring out which patient’s bed alert is sounding. We expect research to show that the Palarum PUP™ System takes back that critical time.

2.1 Risk / Benefit Assessment

Risks of Product

- Over-reliance on automation of technology decreasing hourly rounding presence
- System fails to notify staff of stand alert
- Possible skin impression from prolonged use of sock

Mitigation of Each Risk

- Education
- Patient Assessments
- Replacement of Socks
- Socks come with multiple locations with sock sensor placement

Benefits

- Improved patient safety by reducing the number of patient falls. A 25% reduction in patient falls will result in 90 less falls per year in a 200-bed hospital.
- Improved patient outcomes
- Staff is notified immediately when a patient safety event occurs (fall risk patient is up and unattended)
- Reduced alert fatigue. Improved accuracy of the stand detection with innovative pressure sensitive smart textiles. New notification system which alerts only the closest five caregivers, with an escalation protocol, when a fall risk patient is up and automatically terminates the alert when a caregiver enters the room.
- Data & Analytics. The PUP™ Fall Prevention System delivers critical new data to enhance patient care and improve hospital operations.
- Cost Savings. The Palarum LLC, alert system could save one 200 bed hospital approximately \$744,600 dollars each year. Average 200 bed hospital is expected to have 5 patient falls per 1000 patient days. Therefore, an average 200 bed hospital will have 365 falls per year (20% reduction in patient falls (73)/year x \$10,200/ fall).

3 STUDY OBJECTIVES

3.1 Primary Objective

The primary objective of this study is to determine if the fall incidence rate for patients with the intervention, Palarum LLC's, PUP™ (Patient is Up) System is less than the historical incidence rate of patient falls in the units under study.

3.2 Secondary Objectives

Within the context of the Study

- Determine the rate of false alert delivered by the PUP™ System
- Determine the rate of fall related patient safety events
- Determine the average caregiver response time to an alert delivered by the PUP™ System

4 STUDY DESIGN

4.1 Study Overview

- **Problem** - Falls occur at a rate of 5.5 per 1000 patient days in US hospitals. In addition to the human morbidity and mortality costs, falls cost hospitals in excess of \$8 billion in unreimbursed charges. No intervention to date has been shown to significantly reduce that rate.
- **Purpose** - To determine the effectiveness, if any, of the PUP™ Fall Prevention System. The hypothesis is that the System will reduce the fall rate by at least 25% of prior years' average fall rate.
- **Population to be studied** - All fall risk patients, eighteen years old or older, admitted to OSU Brain and Spine Hospital on Floors 8, 9, and 10 until the sample size is reached.
- **Research Design** – Single arm trial
- **Extent of Researcher Interference** - Minimal, only studying events as they normally occur. The PUP™ System will have been previously evaluated and approved for use as the standard of care at the OSU Medical Center Brain and Spine Hospital in accordance with the terms of an agreement between Palarum and OSU Medical Center dated March 28, 2018.
- **Time horizon** - Current.
- **Study setting** - Non-contrived. OSU Medical Center Brain and Spine Hospital.
- **Measurement and measures**
 - Patient fall rate (measured as number of falls/1000 patient days) data collection and reporting forms, criteria and protocols for the three calendar years preceding initiation of the research.
 - Patient fall rate data collection and reporting forms, criteria, and protocols for the research period calendar year.
 - Data collection standards and protocol for/of;
 - Positive stand detection alert
 - Negative stand detection alert
 - Participant inclusion, exclusion or exemption
 - Sampling methods of 1-3 above
 - Report form(s), structure and content
 - Participant or data exclusion standards, if any.
- **Data Collection Method** - Unobtrusive automated physical measurement using the PUP™ sock, sensors, wireless technology, and REDCap.

4.2 Research Procedures & Steps

- **Pre-Conditions**
 - All Nurses/applicable staff Trained on Palarum System
 - All Equipment Installed in Rooms
 - At Beginning of Shift Nurses Wearing Smart Notification Devices & Enrolled into Unit
- **Patient Admission**
 - Patient Admitted into Room with Palarum Technology
- **Fall Risk Screening**
 - Patient undergoes fall risk assessment.
 - If patient is determined to be fall risk, they proceed to next step
- **Determination of Inclusion/Exclusion Criteria**
 - Containment - Hospital Specific
 - Weight Limit – Hospital Specific
 - Mental Cognizance – Hospital Specific
 - Other Health Conditions – Hospital Specific
- **Registration into Study**
 - If patient is determined as candidate for study and patient and/or LAR has provided written informed consent, then that patient will be registered as a study participant.
- **Patient Education**
 - Patient and/or Patient family will be educated on admission using a video on the in-room tablets.
- **Fit with Sock**
 - Upon registration into study the patient will be fitted for a sock by the nursing staff.
 - Nursing staff utilizes sizing chart to correlate patient's foot size with Palarum Sock size.
 - Sock is placed on patient
- **Enroll Sock in Application**
 - Once sock is successfully fitted on patient the nurse proceeds to enroll the patient through Palarum Application.
 - The following categories must be completed before proceeding to a successful enrollment: Patient Name/Initials/MRN, Sex, Weight, Sock Size, Sensor.

- Upon successful sock pairing to IRT the enrollment process is complete and the patient is now being monitored.
- **Application Records/Data**
 - Enrollment Data
- **Event Logs**
 - Time of stand alert
 - Time to clear
 - Who cleared stand
 - Manual or Automatic termination
 - Accelerator and Gyroscopic Data surrounding each stand event
- **Report Generation**
 - At 12am each morning a report is generated detailing the previous day's activity on the system.
 - Two separate reports are sent each morning at 12am (filtered by audience): Nurse Manager, Site Executive.
 - The reports show: the Pod the patient is enrolled in, # of Alerts during their length of stay, whether a patient has alerted 3 or more times in less than 24 hours.
- **Alert Generation**
 - An alert is generated when a patient places their foot on the ground and takes a step.
 - False alerts are prevented through the use of a gyroscope and accelerometer.
 - Once an alert is generated it is sent to the IRT, HUC, and Smart Notification Devices.
- **How to respond to Alerts**
 - There are two ways to respond to an alert in the Palarum Fall Prevention System
 - Nurse proceeds into the room (wearing Palarum Smart Notification Device) and the system automatically turns off due to his/her proximity.
 - Nurse proceeds into the room and manually turns off the system on the IRT by touching the red alert Icon on the screen and proceeding to put in their initials.

5 CRITERIA FOR EVALUATION

5.1 Primary Effectiveness Endpoint

The primary endpoint is the fall rate per patient days within the study population. A fall is defined as “*an unplanned descent to the floor with or without injury to the patient. Include falls when a patient lands on a surface where you wouldn't expect to find a patient. All unassisted and assisted falls are to be included whether they result from physiological reasons (fainting) or environmental reasons (slippery floor). Also report patients that roll off a low bed onto a mat as a fall.*”

5.2 Secondary Effectiveness Endpoints

- The rate of false alerts per patient days delivered by the PUP™ System. We define as false alert as an alert generated by other than a physical stand by the PUP™ System.
- The number of patient safety events. Fall related patient safety events include patient standing, walking, and otherwise moving without a caregiver present.
- We will assess the average time to respond to an alert delivered by the PUP™ System. This will be the time from the initiation of an alert until it is silenced automatically by RSSI proximity of a caregiver or manually by the caregiver.

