13.3 Analysis of Secondary Endpoints

Secondary outcomes include estimating the incidence of false alerts, the rate of alerts sent out per patient days, characteristics of the patient safety events, and time to response. The analyses of the secondary endpoints will be descriptive and exploratory with the goal of further characterizing the properties of the PUP™ System. Rates and means will be calculated as appropriate. Confidence intervals will be computed to accompany each estimate. No formal statistical testing will be conducted.

We will also examine how fall rates may be associated with patient characteristics. We may also explore data related to the activity level of fall risk patients that are collected by the PUP™ System. These descriptive analyses could help to further characterize the fall risk patient population.

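### The false-alert endpoint in Section 5.2 is a rate per patient-day, so it cannot be compared directly with the synopsis target of under 5%

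*Protocol*

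**What the plan says.** The secondary objectives in the protocol synopsis set two percentage targets. The first reads "To reduce the incidence of false alerts, <5%. Our goal is a high reliability notification system". The second begins "To provide positive alert reliability of 95" (per cent) and goes on to ask how many alerts are sent and how often fall-risk patients are up unassisted.

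The endpoint text uses a different scale or gives none:

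- Section 5.2 gives the endpoint as "The rate of false alerts per patient days delivered by the PUP™ System" and defines a false alert as "an alert generated by other than a physical stand by the PUP™ System".
- The synopsis endpoint list says only "Rate of false alerts", and Section 3.2 only "Determine the rate of false alert delivered by the PUP™ System". Neither gives a denominator, and Section 3.2 gives no target.
- Section 13.3 says "Secondary outcomes include estimating the incidence of false alerts, the rate of alerts sent out per patient days". These are separate estimates, each with a confidence interval. No ratio of the two and no comparison with either target is described, and formal testing is ruled out.

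Positive alert reliability is not defined anywhere and has no matching endpoint in Section 5.2. The SAP, under Study Objectives, repeats both targets and records that no data were collected for either.

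**The concern.** A target of under 5% is naturally read as a share of alerts: of every 100 alerts, fewer than 5 should be false. Section 5.2 instead counts false alerts over time at risk. That quantity depends on how often the system alerts as well as on how often an alert is wrong. On a ward where patients stand often, a device with a small share of false alerts can still produce a high rate per patient-day. On a quiet ward, a poor device can produce a low one.

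An analyst who follows Section 5.2 exactly therefore obtains a number that, taken alone, neither meets nor misses the target. At stake is whether the reliability goal, which the protocol links to alert fatigue, can be read from the reported result.

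**Working it through.** The documents give no computed figure for this endpoint, so there is none to reproduce. The check is one of units.

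**Inputs**

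- F = false alerts per patient-day (Section 5.2).
- A = all alerts per patient-day (Section 13.3). The documents give no expected value, so it is varied.
- Target = 5% (synopsis), taken as a share of alerts. The synopsis states no denominator, so this is an assumption.

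**Identity**

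Share of alerts that are false = F / A, so the value of F equal to the target is 0.05 × A.

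**Results for F = 0.10**

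| A (alerts per patient-day) | Share false = 0.10 / A | F equal to 5% = 0.05 × A |
|---|---|---|
| 0.5 | 20% | 0.025 |
| 1 | 10% | 0.05 |
| 2 | 5% | 0.10 |
| 5 | 2% | 0.25 |
| 10 | 1% | 0.50 |

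The same endpoint value lies above, at or below the target depending on A. No single per-patient-day value corresponds to 5%.

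**Illustration from the SAP**

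The SAP reports 4,999 stands and 2211.6 patient-days, so 4,999 / 2211.6 = 2.26 stands per patient-day.

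- If all alerts ran at that rate, 5% would equal 0.05 × 2.26 = 0.113 false alerts per patient-day.
- If the stands were all true alerts, with false alerts additional to them, then F / (2.26 + F) = 0.05. This gives F = 2.26 × 0.05 / 0.95 = 0.119 per patient-day.

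The documents do not say which reading of the stand count applies, and they state neither threshold. The patient-days run from first enrollment to last unenrollment after cleaning of multiple entries, so they may include gaps in monitoring. These two figures show scale only.

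**Positive alert reliability**

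- If it means true alerts / all alerts, it equals 1 − F/A, and 95% is the complement of 5%.
- If it means stands detected / all stands, it needs a count of missed stands. No endpoint supplies one, and F and A do not determine it.

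**The case against.** The strongest reply is that the information needed is already planned. The system records all alerts, Section 13.3 estimates alerts per patient-day, and dividing the false-alert rate by that rate gives the proportion. This stands. A reader might infer that the objective cannot be answered at all; the documents do not support that, because only the division and the comparison are left unstated.

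Second, patient-days are attached to false alerts in Section 5.2 alone. The other passages say rate or incidence without a denominator. That is also right, but Section 5.2 is where the endpoint is defined, and no other passage gives a proportion.

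Third, nothing is decided on this result. Section 3.2 asks only for the rate to be determined, Section 13.3 is descriptive, and the SAP has no data. This limits the consequence but does not put the endpoint on the target's scale.

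Other stronger readings also fail:

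- A reader might infer that the first two secondary objectives are wholly unanswerable. The counts of alerts and of patient safety events in the second objective are covered by Sections 5.2 and 13.3 and are unaffected.
- A reader might infer that length of stay distorts the rate. Patient-days already adjust for it; the dependence is on alert frequency.
- A reader might infer that the 95% target simply mirrors the 5% target. That holds under only one of two possible meanings.
- A reader might expect 0.05 per patient-day to be taken for 5%. No passage invites that.

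**Conclusion.** The point holds as a mismatch between the endpoint in Section 5.2 and the percentage target in the synopsis. As defined, the endpoint cannot be compared directly with 5%: across 0.5 to 10 alerts per patient-day, a rate of 0.10 corresponds to anything from 20% down to 1% of alerts. The proportion is recoverable from quantities the plan already intends to estimate, so this is a repairable definition and not a lost objective. The conclusion assumes that the 5% is a share of alerts. For the 95% target the documents support only the statement that it is undefined.

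Priority is low. The endpoint is secondary, descriptive and untested, and the SAP reports no data for it. Nothing here shows that the device met or missed either target.

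**What to change.** - **Sections 5.2 and 13.3:** define the false-alert endpoint as false alerts divided by all alerts classified in the manual audit that the synopsis names. Report it with a confidence interval, read descriptively against 5%. If only some alerts are audited, the audited sample should be representative of all alerts.
- **Interval:** allow for repeated alerts per patient where alerts can be linked to patients. The SAP has 4,999 stands and 569 patients, about 8.8 each (4,999 / 569). The event variables it lists include room, unit and bed but no patient identifier, so the link would have to be made or its absence stated.
- **Per-patient-day rate:** keep it as a descriptive measure of alert burden.
- **Positive alert reliability:** define it separately, with its own numerator and denominator. If it means the share of stands detected, say how missed stands are to be counted.
- **Reporting:** as no data were collected, state plainly that the under-5% and 95% targets were not assessed.

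The wording costs a few lines in two sections. Alerts are already logged and an audit is already named, so the definition adds no new type of data, unless reliability is defined by missed stands. Classifying alerts does take audit work, and the SAP indicates that no such data are available for this trial. Here the practical change is the statement that the targets were not assessed.
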